9.2.2 Serious adverse events (SAEs)

A serious adverse event is any untoward medical occurrence or effect that

- results in death;
- is life threatening (at the time of the event);
- requires hospitalisation or prolongation of existing inpatients' hospitalisation;
- results in persistent or significant disability or incapacity;
- is a congenital anomaly or birth defect; or
- any other important medical event that did not result in any of the outcomes listed above due to medical or surgical intervention but could have been based upon appropriate judgement by the investigator.

An elective hospital admission will not be considered as a serious adverse event.

The investigator will report all SAEs to the sponsor without undue delay after obtaining knowledge of the event. The sponsor will report the SAEs through the web portal *ToetsingOnline* to the accredited METC that approved the protocol, within 7 days of first knowledge for SAEs that result in death or are life threatening followed by a period of maximum of 8 days to complete the initial preliminary report. All other SAEs will be reported within a period of maximum 15 days after the sponsor has first knowledge of the serious adverse events.

9.2.3 Suspected unexpected serious adverse reactions (SUSARs)

Not applicable

9.3 Annual safety report

Not applicable

9.4 Follow-up of adverse events

All AEs will be followed until they have abated, or until a stable situation has been reached. Depending on the event, follow up may require additional tests or medical procedures as indicated, and/or referral to the general physician or a medical specialist.

SAEs need to be reported till end of study within the Netherlands, as defined in the protocol

9.5 [Data Safety Monitoring Board (DSMB) / Safety Committee]

Not applicable as this is a feasibility study with no medicinal investigational product.

10. STATISTICAL ANALYSIS

Analysis and statistics will be performed in the Radboud university medical center using Statistical Package for the Social Sciences (IBM SPSS Statistics version 20.0 or higher, SPSS inc., Chicago, Illinois, USA). P values <0.05 will be regarded as statistically significant. Normally distributed continuous variables will be described using mean and standard deviation (SD). Median and interquartile values will be shown in case variables are not normally distributed. The qualitative or categorical variables, i.e. baseline parameters, will be described using frequencies and percentages.

10.1 Primary study parameter(s)

Depending on whether values are normally distributed, different tests will be executed for self-efficacy values obtained through the ESES questionnaire.

Normally distributed: Self-efficacy values between groups will be compared with paired samples t-test (within and between control or intervention group). These tests will be performed between “before” and “after” self-efficacy values of both control and intervention group.

Not normally distributed: Self-efficacy values between groups will be compared with either a Wilcoxon signed rank test (within and between control or intervention group).

These tests will be performed between “before” and “after” self-efficacy values of both control and intervention group.

As exploratory analyses, self-efficacy values will be correlated with system usability, frequency of use (e.g. using the Pearson or Spearman’s rho test, depending on normality of the values) or tested for differences within demographic parameters (independent samples t-tests and/or linear regression).

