4.4 Sample size calculation

This project primarily aims to provide an insight and preliminary evaluation of utilizing NFC-equipped stickers to increase self-efficacy in home exercise programmes. As this is an exploratory pilot study, no formal power analysis has been conducted. We aim to include 30 patients spread across control and intervention group. This includes patients with a lower extremity amputation and Neuralgic Amyotrophic patients. If the pilot is successful, the data provided can be used to expand the research and calculate a sample size for randomized controlled trials.

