8.2 Randomisation, blinding and treatment allocation

We will randomise the allocation of patients to study groups as much as possible within the patient (and NFC) availability pool. Blinding is not appropriate for this pilot.

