8.5 Replacement of individual subjects after withdrawal

Given that this is a feasibility trial, dropouts will not be replaced.

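### Section 10.1 lets an unspecified normality check choose the primary test, and both candidate tests are paired, so neither validly compares the two independent arms

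*Protocol*

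**What the plan says.** Section 2 of the protocol sets a comparative primary objective: whether the sticky reminders raise exercise self-efficacy over 4 weeks relative to usual care. Section 10.1 gives the analysis. It opens with a switch: "Depending on whether values are normally distributed, different tests will be executed for self-efficacy values obtained through the ESES questionnaire". The first branch reads: "Normally distributed: Self-efficacy values between groups will be compared with paired samples t-test (within and between control or intervention group". In the second branch the values are to be "compared with either a Wilcoxon signed rank test (within and between control or intervention group"; the word "either" is followed by only one test. Both branches add that the tests run between the before and after "self-efficacy values of both control and intervention group".

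Section 10 sets significance at p < 0.05 and applies the same normality switch to the summaries (mean and SD, or median and interquartile values). On numbers, section 4.4 says "We aim to include 30 patients spread across control and intervention group", with no ratio. On allocation, section 8.2 says "We will randomise the allocation of patients to study groups as much as possible within the patient (and NFC) availability pool", and section 4.2 concedes that the study is not truly randomised, because patients without an NFC phone can enter only the control arm. Section 8.5 adds: "Given that this is a feasibility trial, dropouts will not be replaced". Section 8.3 describes the ESES as 10 items with a total from 10 to 40, collected before and after in both arms.

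**The concern.** There are two linked faults.

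- **The rule does not fix a test or an estimand.** The before and after scores in two arms make four sets of values, or two sets of changes. The text does not say which must look normal or what follows if they disagree. One branch targets a mean change, the other a rank-based location of change. These differ when changes are skewed, which is when the switch is meant to operate.
- **Neither branch answers the primary question.** A paired t-test and a signed rank test both need matched observations. Control and intervention patients are different people, and the protocol describes no matching. Removing the switch and keeping either named test would not repair the analysis.

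At stake is the only quantitative answer to the primary objective. There is also a later cost: section 4.4 wants the data to support a sample size for randomised trials. That usually needs a mean difference and an SD, which the switch in section 10 could leave unreported.

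**Working it through.** The protocol gives no power, effect size, SD or error rate for this rule, so there is no stated figure to reproduce.

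**Step 1. Can the named tests be run between arms?** Read literally, a paired test is applied across arms. It needs equal numbers and a pairing; the protocol supplies neither, and with arms of, say, 10 and 20 it cannot be computed. Read charitably, only before-after tests within each arm are meant. Then there are two separate p-values and no estimate of the difference between arms. A significant change in one arm and a non-significant change in the other is not a test of the difference. Neither reading gives a valid between-group comparison.

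**Step 2. How often does the normality check give mixed answers?** Inputs from the protocol: total N = 30 (4.4), two arms measured before and after (10.1), a bounded integer scale from 10 to 40 (8.3). Assumptions: arms of 15/15 or 10/20, Shapiro-Wilk at 5%, before-after correlation 0.6, and the ESES distributions shown. Mixed means that some but not all sets are rejected.

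Analytic anchor for exactly normal data and independent checks:
- four sets, any rejection: 1 − 0.95⁴ = 18.5%
- two sets, exactly one rejection: 2 × 0.05 × 0.95 = 9.5%

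Simulation, 4,000 trials per scenario (the two figures are 15/15 and 10/20):

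| Assumed ESES distribution | Mixed, four raw-score sets | Mixed, two change sets |
|---|---|---|
| Normal, SD 5 | 18.8%, 19.5% | 9.6%, 9.8% |
| Rounded, capped at 40, underlying mean 30, SD 5 | 18.0%, 19.0% | 11.5%, 11.2% |
| Rounded, capped at 40, underlying mean 34, SD 5 | 44.6%, 48.2% | 12.7%, 13.6% |
| Left-skewed near the ceiling | 83.0%, 84.5% | 29.6%, 30.5% |

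The check is also weak. At n = 15, Shapiro-Wilk detected real non-normality in 13% (beta(5,2)), 14% (t, 5 df), 37% (gamma, shape 2), 39% (lognormal, sigma 0.5) and 67% (exponential) of samples.

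**Step 3. Is type I error affected?** The paired tests cannot serve between arms, so a two-sample t-test and a Mann-Whitney test on change stood in. The two-stage rule had type I error of 4.7-5.3%. A fixed t-test had 4.7-5.4% and a fixed rank test 4.2-5.5%. The two tests disagreed on significance in about 1.6-2.5% of null trials. There is no material inflation.

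**Step 4. What does a baseline-adjusted model gain?** With equal before and after variances and similar baselines, the variance relative to a between-arm change-score test is (1 + ρ)/2:
- ρ = 0.7: 0.85, i.e. 15% lower
- ρ = 0.5: 0.75, i.e. 25% lower

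With 15 per arm and a baseline difference of d SDs, the adjusted variance is multiplied by about 1 + (d²/28)/(2/15):
- d = 0.5: 1 + 0.00893/0.1333 = 1.07
- d = 1: 1 + 0.03571/0.1333 = 1.27

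At d = 1 and ρ = 0.7, 0.85 × 1.27 = 1.08, so the gain is gone. At ρ = 0.5, 0.75 × 1.27 = 0.95, so little remains. The two methods then also estimate different things. With an assumed baseline gap of 2.5 points and a slope of 0.6, they differ by (1 − 0.6) × 2.5 = 1 point.

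**The case against.** The strongest reply is that this is an exploratory pilot with no power calculation, that no decision rule hangs on the ESES p-value, and that how normality is judged is detail for a statistical analysis plan, which may exist. Much of this stands. The method and threshold of the check can be left to such a plan, and the pilot setting limits the severity. But the protocol itself fixes the switch and the two paired tests for its primary parameter, and detail about the check would not turn a paired test into a comparison of independent arms.

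A reader might infer more than the documents support:

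- *That the rule inflates false positives.* Step 3 shows that it does not.
- *That mixed answers in nearly half of trials are to be expected.* That figure needs Shapiro-Wilk on four raw-score sets and an assumed mean near the ceiling. The protocol names no normality test and gives no ESES mean or SD. If changes are checked, which is what a paired test requires, the figure is about 10-30%.
- *That the wrong quantity is certainly checked.* The text speaks of ESES values and does not settle whether these are raw scores or changes.
- *That there are 15 patients per arm.* This is only 30/2; no ratio is stated.
- *That the adjusted model is always more precise.* This needs similar baselines, which sections 4.2 and 8.2 do not ensure.

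**Conclusion.** The point holds. As written, section 10.1 yields neither a determined primary test nor a valid comparison between arms for the objective in section 2. The between-arm fault follows from the text alone and needs no assumption. How often the switch is ambiguous does rest on assumptions: roughly 10-30% of trials if the two change sets are checked and 18-85% if the four raw-score sets are, with Shapiro-Wilk at 5%, correlation 0.6 and the distributions listed. For an exploratory pilot this is something that should be corrected, not a fatal flaw.

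**What to change.** Rewrite section 10.1 around one pre-stated primary analysis, whatever the distribution looks like:

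- **Primary:** a linear model of 4-week ESES on group and baseline ESES, reported as an adjusted mean difference with 95% CI.
- **Sensitivity:** a rank-based or bootstrap between-arm result, and a between-arm comparison of change scores.
- **Descriptive only:** before-after paired tests within each arm.
- **Summaries (section 10):** always give mean and SD for ESES, with medians in addition if wanted.
- **Interpretation:** state that allocation depends partly on phone availability, so the adjusted difference is not a fully randomised effect, and that a large baseline imbalance can remove the precision gain and separate the adjusted from the change-score estimate.

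The cost is one rewritten paragraph. ESES is already collected at both times in both arms, and the model runs in SPSS, the package named in section 10.

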2. OBJECTIVES

Primary Objective:

To study whether NFC-equipped sticky reminders increase physiotherapy self-efficacy in home exercise programmes as compared to usual care in rehabilitating patients suffering from Neuralgic Amyotrophy or a lower extremity amputation over a period of 4 weeks.

Secondary Objective(s):

To assess the usability of the app and user experiences with NFC-equipped sticky reminders for home exercise programmes in physiotherapy as perceived by rehabilitating patients suffering from Neuralgic Amyotrophy or a lower extremity amputation and how this could be improved.

Other Objective(s)

To determine whether the intervention is used, and thus whether observed effects in intervention group could be caused by the intervention.

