3. STUDY DESIGN

This pilot is a controlled mixed methods feasibility trial.

The Radboudumc department REshape & Innovation Center in collaboration with two physiotherapy departments will execute the pilot. The envisioned duration of the project is five months. Patients will be included in April and May 2018, after which we will analyse data and publish results. The product-testing period is 4 weeks per patient. There will be an intervention group and a control group. The control group will only execute point 1 and 5 in the research design described below besides their regular treatment (excluding interview and SUS component). The control group is present to exclude conclusions based on treatment effects instead of intervention effects. The intervention group will go through all five steps. Millen et al. chose a similar study design, where they measured self-efficacy in cardiac rehabilitation (Millen *et al.*, 2009).

In the present course of therapy, supporting their home exercise program, patients suffering from Neuralgic Amyotrophy or a lower extremity amputation (using a socket or an osseointegrated prosthesis) receive a folder with written instructions on performing the exercises which can be consulted when needed. Patients give feedback during every hospital visit regarding their exercises and progression. In these sessions, the physiotherapist asks for information on the whole week schedule, whereas for patients it is hard to remember the exercises of the beginning of the week. To improve this, the osseointegrated prostheses patients keep a daily paper-based diary for pain scale, pain location, prosthesis wearing time and time spent on muscle exercises and standing or walking. Apart from this, patients do not register or monitor their progress in current course of therapy.

The introduction of the sticky reminders in combination with the app alters the method of registration compared to the present course, but the overall process remains the same. *Instead of written or spoken instructions and feedback, this information will be digitally provided and available.*

The patient process is described and depicted below.

1. **Baseline measurement:** To monitor self-efficacy patients are asked to fill out a validated self-efficacy questionnaire. This outcome is supposed to be the baseline value of the pilot. For extra information regarding the patient, demographic questions will be included in the questionnaire.

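### Section 10.1 assigns paired tests to the comparison between two groups of different patients, and names no independent-groups test for the primary contrast with usual care

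*Protocol*

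**What the plan says.** The primary objective (Protocol section 2) is a comparison between groups: whether the reminders "increase physiotherapy self-efficacy in home exercise programmes as compared to usual care" over 4 weeks. Section 3 describes a parallel design: "There will be an intervention group and a control group". On allocation, section 8.2 says: "We will randomise the allocation of patients to study groups as much as possible within the patient (and NFC) availability pool". No section describes matching, crossover or a rule for pairing a patient in one group with a patient in the other.

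Section 10.1 gives the tests for the ESES score. For normally distributed values: "Self-efficacy values between groups will be compared with paired samples t-test (within and between control or intervention group". Otherwise the values are to be "compared with either a Wilcoxon signed rank test (within and between control or intervention group". Each branch is followed by a sentence saying that the tests are run between the before and after values of both groups.

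Independent-samples methods appear only in the exploratory part of 10.1, where self-efficacy is to be "tested for differences within demographic parameters (independent samples t-tests and/or linear regression", and again for demography in 10.3.

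**The concern.** A paired t-test or signed-rank test needs two values that belong together, normally from the same patient. That holds for before and after within a group. It does not hold between the control and intervention groups. The protocol therefore fixes a test that does not fit its design, and does so for the comparison that the primary objective asks about. This is a wrong stated rule, not detail left to a statistical analysis plan; a later plan would have to contradict the protocol to correct it.

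At stake is the one quantitative answer the pilot is meant to give. Section 10 sets P below 0.05 as the criterion for significance, and section 4.4 expects the data to help size later randomised trials.

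**Working it through.** **Inputs from the protocol.** Total target 30 patients, with no split between groups (4.4). Significance at P < 0.05 (10), taken as two-sided. Patients without an NFC-compatible phone can enter only the control group (4.2). Dropouts are not replaced (8.5). The protocol gives no effect size, SD or power, so it has no figure to reproduce.

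**Assumptions.** 15 patients per group, normal data, and one value per patient in units of the SD (for example a change score).

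**1. Unequal groups.** A paired test needs the same number of values in each group. With a split such as 18 and 12, six control patients would have to be dropped. The entry rule in 4.2 and unreplaced dropouts make an exactly equal split unlikely.

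**2. Equal groups.** With n per group, SDs of 1 and observed difference d:

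- independent test: t = d / √(2/n), df = 2n − 2 = 28, critical value 2.048
- paired test: t = d / √((2 − 2r)/n), df = n − 1 = 14, critical value 2.145

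Here r is the accidental correlation created by the order in which patients are listed.

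Take one dataset with d = 0.75. The independent test gives t = 0.75 / √(2/15) = 2.054, p = 0.049. The paired test on the same patients gives:

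| Accidental r | Paired t | p (df 14) |
|---|---|---|
| +0.524 | 2.054/√0.476 = 2.977 | 0.010 |
| 0 | 2.054 | 0.059 |
| −0.524 | 2.054/√1.524 = 1.664 | 0.118 |

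Under random ordering r has SD 1/√14 = 0.267, so ±0.524 (1.96 × 0.267) spans about 95% of orderings. The paired test is significant when r exceeds 1 − (2.054/2.145)² = 0.083, which happens in about 38% of orderings. Simulating 10,000 re-orderings of one such dataset agrees: central 95% range of p 0.011 to 0.117, below 0.05 in 38%. The signed-rank p has a central 95% range of 0.010 to 0.188.

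**3. Typical size of the row-order effect.** Over simulated datasets with a true difference of 0.8 SD, the median 5th and 95th percentiles of the paired p over pairings are about 0.01 and 0.08 (separate runs: 0.009 to 0.073, 0.011 to 0.084, 0.010 to 0.080). In 32% to 35% of datasets the verdict at 0.05 depends on row order, meaning that between 5% and 95% of pairings are significant.

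**4. Error rate and power.** If the pairing ignores the data, type I error is 0.050 paired and 0.049 independent. Power at 0.8 SD is 0.53 paired and 0.56 independent.

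**5. The other reading: within-group tests only.** Suppose both groups truly improve by 0.5 SD of the change score. Each before/after t-test with 15 patients is significant with probability 0.44. The chance that the intervention group is significant and the control group is not is 0.44 × (1 − 0.44) = 0.246, about 25%. The chance that the two verdicts disagree in either direction is 2 × 0.246 = 0.49. Simulation gives 0.247 and 0.491.

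**The case against.** The best defence is the sentence on before and after values that closes each branch of 10.1. It describes a within-patient comparison, for which both tests are correct. With data entered one row per patient, a paired procedure would produce exactly that. In the signed-rank sentence the word either has no second alternative, which suggests that a test may have been lost in drafting. The authors also name independent-samples tests elsewhere. Faulty wording is thus at least as likely as an intention to pair unrelated patients, and the documents do not establish such an intention.

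This stands as an account of what may have been meant, but it does not repair the plan. Both branches state the between-group use explicitly. If that use is set aside, the primary objective has no between-group test, with the consequence in step 5.

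A reader might go further and infer that the between-group p-value means nothing or that false positives are inflated. The documents do not support that. With equal groups and a pairing that ignores the data, the 5% level holds and little power is lost (step 4). Serious inflation would require each group to be sorted by score before pairing, and nothing in the protocol suggests this.

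The study is also an unpowered exploratory pilot, and section 4.2 concedes that it is not truly randomised. Even a correct test would therefore give a result open to confounding. That lowers the consequence of the error without removing it.

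**Conclusion.** The point holds in a limited form. Paired tests are right within each group and wrong between groups, and no suitable between-group test is named for the primary contrast. Read literally, the comparison either discards patients or yields a p-value that depends on listing order. Read charitably, the comparison with usual care is not tested at all.

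The error itself follows from the text and needs no assumption. The sizes do: they rest on 15 patients per group, normal data, and true values of 0.8 SD (row-order effect) or 0.5 SD (within-group contrast), none of which the protocol states. A different split or effect would change the percentages.

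**What to change.** In section 10.1:

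- Limit the paired t-test and the signed-rank test to before/after change within each group, and delete the reference to between-group use from both sentences.
- Name one independent-groups comparison for the primary contrast. Acceptable choices are an independent-samples t-test or a Mann-Whitney test on individual ESES change scores, or a linear model of week-4 ESES on group and baseline ESES. Change-score and baseline-adjusted analyses can answer different questions when allocation is not fully random, so the choice should be made in advance and briefly justified.
- Report the result as a difference between groups with a confidence interval, and state that it is exploratory because allocation is not fully random.

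The cost is one paragraph of protocol wording. No extra data or patients are needed.

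### Section 10.1 announces a comparison between the arms but assigns it only paired tests, so no valid test of the primary objective is named

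*Protocol*

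**What the plan says.** Section 2 makes the primary question comparative: whether the reminders "increase physiotherapy self-efficacy in home exercise programmes as compared to usual care". Section 3 gives the reason for having a second arm: "The control group is present to exclude conclusions based on treatment effects instead of intervention effects".

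Section 10.1 then names one test for each distributional case.

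- Normal: "Self-efficacy values between groups will be compared with paired samples t-test (within and between control or intervention group").
- Not normal: "Self-efficacy values between groups will be compared with either a Wilcoxon signed rank test (within and between control or intervention group").
- Both cases: the tests are run on the before and after "self-efficacy values of both control and intervention group".

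Section 10 adds the threshold: "P values <0.05 will be regarded as statistically significant". Section 10.1 mentions methods for independent groups only among the exploratory analyses, where self-efficacy is "tested for differences within demographic parameters (independent samples t-tests and/or linear regression"). Section 10.3 repeats this for the demographic categories.

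Section 4.4 aims for 30 patients over both groups, gives no split and reports no power calculation. Sections 4.2 and 8.2 make clear that allocation is random only as far as possession of an NFC phone allows.

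**The concern.** A paired test needs a natural link between the two values in each pair. Before and after scores of one patient have such a link; a control patient and an intervention patient do not. Section 10.1 therefore promises a between-group comparison and gives it a test that does not fit. It also leaves open what is to be compared between the arms: week-4 scores, changes or something else.

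What can validly be run as written is a before/after test in each arm. All participants are in active rehabilitation, so self-efficacy may rise in both arms whether or not the app works. A significant rise in one arm and a non-significant one in the other does not show that the arms differ. Reading the result that way would bring back the confusion that the control group was meant to remove.

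Section 4.4 also intends the data for sizing later randomised trials. That needs an arm difference with its uncertainty, and within-arm p-values do not give one.

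**Working it through.** The plan gives no power, SD or effect size, so there is no figure of its own to reproduce. The check has three parts.

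**1. Paired tests across arms.** With unequal arms, a paired test cannot be run across them. With 15/15 it can be run only after an arbitrary pairing. In a simulation of 300 data sets with a true difference of 0.5 SD, each re-paired 100 times, significance at 0.05 depended on the pairing order in about 42%. With no true difference and one arbitrary pairing fixed in advance, the false-positive rate was 4.8%. The trouble is thus not an inflated error rate but a result that the data do not determine.

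**2. Within-arm tests read side by side.**

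From the protocol: total 30 (Section 4.4) and threshold 0.05 (Section 10). Assumed: two-sided tests; splits 15/15, 20/10 and 10/20 (intervention/control); the same true rise in both arms of 0.1-0.8 SD of the score; before/after correlation r of 0.3-0.7; no app effect.

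- SD of change = √(2(1−r)), in SD of the score.
- Standardised change d = rise / √(2(1−r)).
- Power of each arm's test: noncentral t, n−1 degrees of freedom, noncentrality d√n.
- P(intervention significantly up, control not) = P(intervention significantly up) × (1 − P(control significant)).

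Example at 15/15, rise 0.5 SD, r = 0.5: SD of change = √(2 × 0.5) = 1, d = 0.5, noncentrality 0.5 × √15 = 1.94, power 0.438. The discordant result has probability 0.438 × (1 − 0.438) = 0.246.

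Results at r = 0.5, where d equals the rise:

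| Common rise (SD) | 15/15 | 20/10 | 10/20 |
|---|---|---|---|
| 0.1 | 5.1% | 5.9% | 4.4% |
| 0.2 | 9.6% | 12.2% | 7.1% |
| 0.3 | 15.4% | 21.3% | 10.1% |
| 0.5 | 24.6% | 39.9% | 12.8% |
| 0.6 | 24.4% | 43.6% | 11.0% |
| 0.8 | 14.7% | 35.5% | 4.7% |

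Over r = 0.3-0.7 and rises of 0.1-0.8 SD, the full ranges are:

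- 15/15: 3.8% to 24.8%. With equal arms the quantity is essentially p(1−p), which cannot exceed 25%.
- 20/10: 5.2% to 43.6%.
- 10/20: 0.7% to 12.8%.

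The benchmark is 2.5%: the chance that one valid two-sided 0.05 test between comparable arms wrongly favours the app. With no common rise the discordant result has probability 0.025 × 0.95 = 0.024, so the shared trend causes the excess. At 10/20 with r = 0.7 and a rise of 0.7-0.8 SD the figure falls below 2.5% (2.2% and 0.7%), because the control arm is then nearly always significant.

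**3. Valid between-arm contrasts at 15/15.** Variance per patient, in SD² of the score, is 2(1−r) for change scores and 1−r² after adjustment for baseline.

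| r | Change score: variance | 95% CI half-width | Power at 0.5 SD | Baseline-adjusted: variance | 95% CI half-width | Power at 0.5 SD |
|---|---|---|---|---|---|---|
| 0.3 | 1.40 | 0.89 SD | 20% | 0.91 | 0.71 SD | 28% |
| 0.5 | 1.00 | 0.75 SD | 26% | 0.75 | 0.65 SD | 33% |
| 0.7 | 0.60 | 0.58 SD | 40% | 0.51 | 0.54 SD | 46% |

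Both contrasts cancel a rehabilitation trend common to the arms. The adjusted one is the more precise at each r.

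**The case against.** The sponsor can fairly say that Section 10.1 does plan a between-group comparison, since it says so for both the normal and the non-normal case. In the non-normal case the word *either* has no second option after it, which suggests that a second test dropped out in drafting. This stands against the stronger reading that the plan contains within-arm tests only. It does not rescue the text: the tests named for the comparison are paired ones, and the compared quantity is undefined.

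A reader might also infer that the sponsor will claim efficacy when the intervention arm is significant and the control arm is not. No section states that rule. The error rates above belong to a reading that the text leaves open, because it names no other valid test. Nor should one narrow slice be taken as the size. A figure of 21-25% follows from 15/15, a rise of 0.4-0.5 SD and r of 0.5-0.7, but the protocol supplies none of these.

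It may be said that the choice of covariates is commonly left to a statistical analysis plan. That is right, and the absence of ANCOVA is not itself an error; an unpaired comparison of change scores would also be valid. It would be tempting to express the gain from adjustment as extra patients. At r = 0.6, 30/0.64 is about 47, but that rests on one assumed correlation and on a week-4-only comparison that the plan does not specify.

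Finally, this is an exploratory pilot that admits its allocation limits. That lowers the stakes, but the protocol still sets a comparative primary objective and a significance threshold.

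**Conclusion.** Wrong as written. Section 10.1 gives a comparison of independent arms to tests for paired data, so the plan names no valid test of its primary objective. This rests on the text alone and needs no assumption.

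The numerical consequence is conditional. If within-arm p-values are set side by side, the chance of an apparent app effect when there is none is about 4-25% at 15/15, 5-44% at 20/10 and 1-13% at 10/20, against 2.5%. It exceeds 2.5% nearly everywhere in the range examined, but its size depends on the split, the common rise and the correlation, all of which are assumed.

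Baseline adjustment would deal with imbalance in baseline ESES. It would not remove other confounding by phone ownership, since patients without an NFC phone can enter only the control group.

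**What to change.** In Section 10.1, replace the between-group use of the paired tests with one independent-groups contrast.

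- **Primary:** the difference between arms in week-4 ESES, adjusted for baseline ESES (ANCOVA), with its 95% CI.
- **Sensitivity:** an unpaired comparison of change scores. It is worth having because allocation is not truly random, and with non-random groups the two analyses can disagree. If a rank-based fallback is kept, it should also be an unpaired test.
- **Within arm:** report before/after changes descriptively, and draw no comparison of the arms from their p-values.
- **Limitation:** state that adjustment for baseline ESES does not remove other differences linked to owning an NFC phone.

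The cost is wording only. Section 8.3 already has ESES collected at the start and at the end in both arms.
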